### **5.2.2. Analyses for Continuous Data**

Unless otherwise stated, descriptive statistics for continuous variables are n, mean, median, standard deviation, minimum, and maximum.

#### **5.2.2.1. Geometric Means**

For immunogenicity results of serotype-specific IgG concentrations, OPA titers and the antibody levels of the concomitant vaccines, the geometric means will be computed along with associated 95% CIs. The GM and associated 2-sided 95% CI will be calculated as the mean of the assay results on the natural logarithmic scale based on the t-distribution, and then exponentiating the results.

#### **5.2.2.2. Geometric Mean Ratios**

Where appropriate, GMRs and their 2-sided 95% CIs will be derived by calculating differences in means and CIs on the natural log scale of the assay results based on the t-distribution (allowing for unequal variances), and then exponentiating the results. The difference in means, on the natural log scale, will be the 20vPnC group minus the 13vPnC group.

#### **5.2.2.3. Geometric Mean Fold Rises**

The GMFRs will be calculated by exponentiating the mean of the difference of logarithmically transformed assay results (later minus earlier). The associated 2-sided 95% CIs are computed by exponentiating the limits of CIs obtained using Student's t-distribution for the mean difference on the natural log scale.

CCI

### 5.3. Methods to Manage Missing Data

A partial AE start date (missing day or missing both month and day) will be imputed by assigning the earliest possible start date using all available information, such as the stop date of the AE and the vaccination date(s) from the same participant, following the Pfizer standard of handling incomplete AE start date. A complete missing start date for an AE is not allowed in the data collection.

The LLOQ for each assay will be provided by Vaccines Research and Development as part of the electronic data transfer or within the Clinical Testing Completion Memo prior to statistical analysis. Assay results above the LLOQ will be reported, and values below the LLOQ, denoted as BLQ, will be imputed as  $0.5 \times \text{LLOQ}$  for analysis.

No additional imputation will be applied to other missing data.

## 6. ANALYSES AND SUMMARIES

### 6.1. Primary Endpoint(s)

#### 6.1.1. Primary Safety Endpoint(s)

##### 6.1.1.1. Local Reactions

Results from local reactions after each dose (Dose 1, Dose 2, Dose 3, and Dose 4) will be summarized separately.

##### 6.1.1.1.1. Main Analysis

- Estimand: The percentage of participants reporting prompted local reactions (redness, swelling, and pain at the injection site) within 7 days after each dose (Section 2.1).
- Analysis set: Safety population (Section 4).
- Analysis time point: Within 7 days after each dose.
- Analysis methodology: The between-group difference (20vPnC – 13vPnC) and the corresponding 2-sided 95% CI will be calculated using the Miettinen and Nurminen method (Section 5.2.1) for each reaction.
- Intercurrent events and missing data: Missing values will not be imputed.  
**CCI**
- Reporting results: Count and percentage of participants with the indicated endpoint and the associated 2-sided 95% CI for each and any local reaction after each dose in each vaccine group will be presented by maximum severity across severity levels. Between-group differences (20vPnC – 13vPnC) in these percentages and their 2-sided 95% CIs will also be provided. The denominator used in the percentage calculation will be the number of participants with any e-diary data reported after vaccination.

CCI [REDACTED]

[REDACTED]

■ [REDACTED]

■ [REDACTED]

[REDACTED]

[REDACTED]

CCI [REDACTED]

[REDACTED]

#### 6.1.1.2. Systemic Events

Results from systemic events after each dose (Dose 1, Dose 2, Dose 3, and Dose 4) will be summarized separately.

##### 6.1.1.2.1. Main Analysis

- Estimand: The percentage of participants reporting prompted systemic events (fever, decreased appetite, irritability, and drowsiness/increased sleep) within 7 days after each dose (Section 2.1).
- Analysis set: Safety population (Section 4).
- Analysis time point: Within 7 days after each dose.
- Analysis methodology: The between-group difference (20vPnC – 13vPnC) and the corresponding 2-sided 95% CI will be calculated using the Miettinen and Nurminen method (Section 5.2.1) for each event.
- Intercurrent events and missing data: Missing values will not be imputed. CCI [REDACTED]

- Reporting results: Count and percentage of participants with the indicated endpoint and the associated 2-sided 95% CI for each and any systemic event after each dose in each vaccine group will be presented by maximum severity across severity levels. Between-group differences (20vPnC – 13vPnC) in these percentages and their 2-sided 95% CIs will also be provided. The denominator used in the percentage calculation will be the number of participants with any e-diary data reported after vaccination.

CCI [REDACTED]

[REDACTED]

■ [REDACTED]

■ [REDACTED]

CCI [REDACTED]

CCI [REDACTED]

[REDACTED]

[REDACTED]

### 6.1.1.3. Adverse Events

#### 6.1.1.3.1. Main Analysis

- Estimands:
  - The percentages of participants reporting AEs from Dose 1 to 1 month after Dose 3 ([Section 2.1](#)).
  - The percentages of participants reporting AEs from Dose 4 to 1 month after Dose 4 ([Section 2.1](#)).
- Analysis set: Safety population ([Section 4](#)).
- Analysis time points: Dose 1 to 1 month after Dose 3 and Dose 4 to 1 month after Dose 4.
- Analysis methodology: 3-Tiered approach as described in [Section 5.2.1](#).

[REDACTED]

[REDACTED]

- Intercurrent events and missing data: No missing values will be imputed except for partial AE start dates ([Section 5.3](#)).
- Reporting results: For all 3 tiers, the numerator (n) and the denominator (N) used in the percentage calculation, the percentage (%), and the corresponding 2-sided 95% CI for participants reporting any AE, by each system organ class and each preferred term within system organ class, will be presented by vaccine group.

In addition, for AEs classified as Tier 2 events, the differences in percentages (20vPnC – 13vPnC) and associated 2-sided 95% CIs will be provided.

Further, for Tier 1 events, if any are identified, the difference in percentages, the associated 2-sided 95% CI for the risk difference, and the asymptotic p-values will also be provided.

CCI [REDACTED]

[REDACTED]

[REDACTED]

CCI [REDACTED]

[REDACTED]

#### 6.1.1.4. Serious Adverse Events and Newly Diagnosed Chronic Medical Conditions

##### 6.1.1.4.1. Main Analyses

- Estimands:
  - The percentage of participants reporting SAEs from Dose 1 to 6 months after Dose 4 ([Section 2.1](#)).
  - The percentage of participants reporting NDCMCs from Dose 1 to 6 months after Dose 4 ([Section 2.1](#)).
- Analysis set: Safety population ([Section 4](#)).
- Analysis time point: Dose 1 to 6 months after Dose 4.

[REDACTED]

[REDACTED]

- Analysis methodology: Descriptive statistics.
- Reporting results: The numerator (n) and the denominator (N) used in the percentage calculation, the percentage (%), and the corresponding 2-sided 95% CI for participants reporting any SAEs/NDCMCs, by each system organ class and each preferred term within system organ class, will be presented by vaccine group. SAEs and NCDMCs will be presented separately.

CCI [REDACTED]

## 6.1.2. Primary Pneumococcal Immunogenicity Endpoints

### 6.1.2.1. Participants With Predefined Pneumococcal Serotype-Specific IgG Concentrations at 1 Month After Dose 3

#### 6.1.2.1.1. Main Analysis

- Estimands:
  - For each of the 13 matched serotypes in 20vPnC, the difference in percentages of participants with predefined serotype-specific IgG concentrations between the 20vPnC and the 13vPnC groups ([Section 2.1](#)).
  - For each of the 7 additional serotypes in 20vPnC, the difference in the percentages of participants with predefined serotype-specific IgG concentrations between the 20vPnC group and the lowest percentage of participants with predefined serotype-specific IgG concentrations among the 13 serotypes from the 13vPnC group, excluding serotype 3.
- Analysis set: Dose 3 evaluable immunogenicity population ([Section 4](#)).
- Analysis time point: 1 Month after Dose 3.
- Analysis methodology: The between-group difference (20vPnC – 13vPnC) and the corresponding 2-sided 95% CI will be calculated using the Miettinen and Nurminen method ([Section 5.2.1](#)) for each serotype. The NI will be assessed by comparing the lower bound of the 95% CI against the NI margin ([Section 5.1.1.1](#)).
- Intercurrent events and missing data: Serology data deemed unevaluable because of noncompliance with the key protocol criteria will be excluded. Missing data will not be imputed.

- Reporting results: For each of the 20 vaccine serotypes, the numerator (n) and the denominator (N) used in the percentage calculation, the percentage (%), and the corresponding 2-sided 95% CI for participants with predefined IgG concentrations from each vaccine group, as well as the percentage difference and the associated 95% CI, will be presented.

### Figures:

A forest plot of between-group differences (20vPnC – 13vPnC) with 95% CIs for the percentages will be presented.

Percentages (and corresponding 95% CIs) of participants achieving predefined serotype-specific IgG concentrations 1 month after Dose 3 will be presented in 2 vertical bar charts, 1 for the 13 matched serotypes and 1 for the 7 additional serotypes.

#### 6.1.2.1.2. Supplementary Analysis

As a supplemental analysis to the main analysis that assesses NI, for each of the 7 additional serotypes, the percentage difference (and its 2-sided 95% CI) between the 2 groups (20vPnC – 13vPnC), with the comparator being the percentage of participants achieving predefined IgG concentrations for that corresponding serotype from the 13vPnC group, will be provided.

As a supportive analysis to the main analysis, an additional summary may be provided using an alternative reference concentration of 0.15 µg/mL for all serotypes.

#### 6.1.2.2. Pneumococcal Serotype-Specific IgG Concentrations 1 Month After Dose 4

##### 6.1.2.2.1. Main Analysis

- Estimands:
  - For each of the 13 matched serotypes in 20vPnC, GMRs of serotype-specific IgG concentrations from the 20vPnC group to the 13vPnC group 1 month after Dose 4 ([Section 2.1](#)).
  - For each of the 7 additional serotypes in 20vPnC, GMRs of serotype-specific IgG concentrations from the 20vPnC group to the lowest IgG GMC among the 13 serotypes from the 13vPnC group, excluding serotype 3.
- Analysis set: Dose 4 evaluable immunogenicity population ([Section 4](#)).
- Analysis time point: 1 Month after Dose 4.
- Analysis methodology: The serotype-specific IgG GMRs of the 20vPnC group to the 13vPnC group and their 2-sided 95% CIs will be derived ([Section 5.2.2.2](#)) based on the t-distribution. The lower limit of the CI will be used in the hypothesis test for NI of 20vPnC to 13vPnC ([Section 5.1.1.2](#)).

- Intercurrent events and missing data: Serology data deemed unevaluable because of noncompliance with the key protocol criteria will be excluded. Concentrations below the LLOQ or denoted as BLQ will be set to  $0.5 \times \text{LLOQ}$  for analysis. Missing data will not be imputed.
- Reporting results: For each of the 20 vaccine serotypes, the GMC and corresponding 2-sided 95% CI from each vaccine group, as well as the GMR of the 20vPnC group to the 13vPnC group and the 2-sided 95% CI, will be presented.

**Figures:**

A forest plot of GMRs with 95% CIs from all 20 serotypes will be presented.

Antibody response curves showing the IgG GMCs, with corresponding 95% CIs, for the 3 blood draw time points will be presented by vaccine group.

GMCs, and corresponding 95% CIs, of serotype-specific IgG concentrations before and 1 month after Dose 4 will be presented in 2 vertical bar charts, 1 for the 13 matched serotypes and 1 for the 7 additional serotypes.

**6.1.2.2.2. Supplementary Analysis**

As a supplementary analysis to support the interpretation of the main analysis, for each of the 7 additional serotypes, the GMR (and its 2-sided 95% CI) of 20vPnC to 13vPnC at 1 month after Dose 4, with the comparator being the IgG GMC of the corresponding serotype in the 13vPnC group, will be calculated.

**6.1.3. Primary Concomitant Immunogenicity Endpoints**

**6.1.3.1. Participants With Prespecified Antibody Levels to Each Concomitant Vaccine Antigen 1 Month After Dose 3**

**6.1.3.1.1. Main Analyses**

- Estimand: Differences in percentages of participants with prespecified antibody levels ([Section 3.1.3](#)) to diphtheria toxoid, tetanus toxoid, pertussis antigens (PT, FHA, PRN), HBsAg, poliovirus strains (types 1, 2, and 3), and Hib at 1 month after Dose 3 between the 20vPnC group and the 13vPnC group ([Section 2.1](#)).
- Analysis set: Dose 3 evaluable immunogenicity population restricted to those who received the corresponding concomitant vaccine with the specified concomitant vaccine antigen ([Section 4](#)).
- Analysis time point: 1 Month after Dose 3.

- Analysis methodology: The between-group difference (20vPnC – 13vPnC) and the corresponding 2-sided 95% CI will be calculated using the Miettinen and Nurminen method (Section 5.2.1). The NI will be assessed by comparing the lower bound of the 95% CI against the NI margin (Section 5.1.1.1).
- Intercurrent events and missing data: Serology data deemed unevaluable because of noncompliance with the key protocol criteria will be excluded. Concentrations below the LLOQ or denoted as BLQ will be set to  $0.5 \times \text{LLOQ}$  for analysis. Missing data will not be imputed.
- Reporting results: For each concomitant vaccine antigen, the numerator (n) and the denominator (N) used in the percentage calculation, the percentage (%), and the corresponding 2-sided 95% CI for participants with prespecified antibody from each vaccine group, as well as the percentage difference and the associated 95% CI, will be presented.

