9.1. Estimands and Statistical Hypotheses

9.1.1. Estimands

The estimand corresponding to each primary, secondary, CCI objective is described in the table in Section 3. The estimands to evaluate the immunogenicity objectives for noninferiority are based on evaluable populations (Section 9.3). These estimands estimate the vaccine effect in the hypothetical setting where participants follow the study schedules and protocol requirements as directed. The estimand addresses the objective of estimating the maximum potential difference between 2 groups, since the impact of noncompliance is likely to diminish the observed difference between the 2 groups. Missing serology results will not be imputed. Immunogenicity results that are below the LLOQ will be set to $0.5 \times \text{LLOQ}$ in the analysis.

In the primary safety objective evaluations, missing e-diary data will not be imputed. Missing AE dates will be imputed according to Pfizer safety rules. No other missing information will be imputed in the safety analysis.

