9.1.3. Multiplicity Considerations

Pneumococcal Immunogenicity Evaluation

For the primary pneumococcal immunogenicity objectives comparing percentages of participants with predefined serotype-specific IgG concentration levels 1 month after Dose 3, noninferiority will be assessed by the hypothesis test as described in [Section 9.1.2.1.1](#) at an alpha level of 0.05 for each serotype. The primary pneumococcal immunogenicity objectives will be achieved if the noninferiority of 20vPnC to 13vPnC for the percentage of participants with the predefined IgG concentration level at 1 month after Dose 3 is established for all 20 serotypes.

For the primary pneumococcal immunogenicity objectives comparing serotype-specific IgG GMCs 1 month after Dose 4, noninferiority will be assessed by the hypothesis test as described in [Section 9.1.2.1.2](#) at an alpha level of 0.05 for each serotype. The primary pneumococcal immunogenicity objectives will be achieved if the noninferiority of the IgG GMCs from the 20vPnC group compared to the 13vPnC group at 1 month after Dose 4 is established for all 20 serotypes.

The overall primary pneumococcal immunogenicity objectives will be achieved if noninferiority of 20vPnC comparing to 13vPnC based on both the percentage of participants with predefined serotype-specific IgG concentration levels at 1 month after Dose 3 and the serotype-specific IgG GMC at 1 month after Dose 4 is demonstrated for all 20 serotypes. Therefore, the overall type I error rate for the primary immunogenicity assessment of the pneumococcal immune response of 20vPnC is well controlled at the 0.05 level.

Concomitant Immunogenicity Evaluation

For the primary concomitant immunogenicity objective comparing immune responses induced by concomitant vaccine antigens at 1 month after Dose 3 from the 20vPnC group to that from the 13vPnC group, noninferiority is assessed by a hypothesis test (Section 9.1.2.2.1) at an alpha level of 0.05 for each concomitant vaccine antigen. The primary concomitant immunogenicity objective will be met if noninferiority is achieved for all concomitant vaccine antigens, diphtheria toxoid, tetanus toxoid, pertussis antigens (PT, FHA, PRN), HBsAg, poliovirus strains, and Hib. Therefore, the type I error rate for the concomitant immunogenicity assessment is well controlled at the 0.05 level.

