### 3.1.3. Primary Concomitant Immunogenicity Endpoints

- Antibody levels to diphtheria toxoid, tetanus toxoid, and pertussis antigens (PT, FHA, PRN) 1 month after Dose 3
- Antibody levels to HBsAg 1 month after Dose 3
- Antibody levels to poliovirus strains (types 1, 2, and 3) 1 month after Dose 3
- Antibody levels to Hib 1 month after Dose 3

Antibody concentrations to each concomitant vaccine will be determined on sera collected 1 month after Dose 3 from a randomly selected subset of participants with sufficient sera volumes. Further details of the subsetting will be described in a memo to the unblinded statistician before any testing proceeds.

To support the primary concomitant immunogenicity estimands, antibody concentrations will be classified based on prespecified antibody thresholds for the concomitant vaccine antigens:

Antigen	Prespecified Level
Diphtheria	$\geq 0.1$ IU/mL
Tetanus	$\geq 0.1$ IU/mL
Acellular pertussis (PT, FHA, PRN)	$\geq$ the observed antipertussis antibody concentration achieved by 95% of 13vPnC recipients
Hepatitis B	$\geq 10$ mIU/mL
Poliomyelitis (types 1, 2, and 3)	$\geq 1:8$
Hib	$\geq 0.15$ $\mu\text{g/mL}$ anti-PRP Alternative: $\geq 1.0$ $\mu\text{g/mL}$ anti-PRP a

a. Secondary concomitant immunogenicity endpoint 1 month after Dose 3.

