### **5.1.2. Concomitant Immunogenicity Hypotheses**

#### **5.1.2.1. Percentage of Participants With Prespecified Antibody Level to Each Concomitant Vaccine Antigen at 1 Month After Dose 3 (Primary Concomitant Immunogenicity Objectives)**

Hypothesis testing to assess NI of the 20vPnC group to the 13vPnC group for percentage of participants with prespecified antibody level to each concomitant vaccine antigen will be performed similarly to that for the percentage of participants with predefined serotype-specific IgG concentrations, as described in [Section 5.1.1.1](#), with  $\pi_{20vPnC}$  and  $\pi_{13vPnC}$  being the percentages of participants with prespecified antibody levels ([Section 3.1.3](#)) to diphtheria toxoid, tetanus toxoid, pertussis antigens (PT, FHA, PRN), HBsAg, poliovirus strains, or Hib at 1 month after Dose 3 from the 20vPnC and 13vPnC groups, respectively.

The null hypothesis will be rejected and NI will be declared for a concomitant vaccine antigen if the lower bound of the 2-sided 95% CI for the difference (20vPnC - 13vPnC) in percentages is greater than -10% (10% NI margin) for that concomitant vaccine antigen.

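### The PT, FHA and PRN cut-off has no floor at the LLOQ: if more than about 5% of tested 13vPnC infants fell below it, noninferiority for that antigen could not fail

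*SAP*

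**What the plan says.** Of the ten primary concomitant tests, seven use fixed antibody levels. The three pertussis tests (PT, FHA, PRN) use a level taken from the trial's own control group: an infant passes at or above "the observed antipertussis antibody concentration achieved by 95% of 13vPnC recipients" (SAP 3.1.3; same definition in protocol 8.1.1 and 9.1.2.2.1).

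The substitution rule for unquantifiable results appears three times, each time with the value 0.5 × LLOQ:
- Protocol 9.1.1: "Immunogenicity results that are below the LLOQ will be set to" that value.
- SAP 5.3: "values below the LLOQ, denoted as BLQ, will be imputed as" that value.
- SAP 6.1.3.1.1, for this analysis: "Concentrations below the LLOQ or denoted as BLQ will be set to" that value.

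The decision rule in SAP 6.1.3.1.1 is "The NI will be assessed by comparing the lower bound of the 95% CI against the NI margin", with a Miettinen-Nurminen interval and a margin of -10 percentage points (SAP 5.1.2.1). Each test is run "at an alpha level of 0.05 for each concomitant vaccine antigen" (protocol 9.1.3), and the objective needs every antigen to pass.

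On the LLOQ, SAP 5.3 says only that "The LLOQ for each assay will be provided by Vaccines Research and Development". No values or expected below-LLOQ rates are given. The visible text does not say how the percentile is computed, or what happens if it falls among substituted values.

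**The concern.** The two rules interact. If fewer than 95% of tested 13vPnC infants have a quantifiable result, the highest analysis value that at least 95% of them reach is the substituted 0.5 × LLOQ. No analysed value can be lower and the criterion is at or above, so every infant in both groups passes. The comparison then no longer depends on the 20vPnC data.

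At stake is the formal conclusion for up to three of the ten primary concomitant tests. An affected antigen would be declared noninferior even if many more 20vPnC infants lacked measurable antibody. The cut-off depends on 13vPnC results and the study team stays blinded until the primary analysis (protocol 9.5.1, SAP 7.2), so a repair made after seeing the problem would be post hoc.

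**Working it through.** **Inputs.** Margin -10%, two-sided 95% Miettinen-Nurminen interval (z = 1.96, so 2z² = 7.683). Sizes per group for 99% power, from protocol Table 5: FHA 212, PT 276, PRN 367. The number of sera actually tested is not stated, so these sizes are assumptions here. True below-LLOQ rates are also assumed, because the documents give none.

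**1. The plan's own figures.** When all n infants pass in both groups, the restricted estimates at a difference of -δ are 1 and 1 - δ. The variance, with the N/(N - 1) factor, is 2δ(1 - δ)/(2n - 1). Solving δ² = z² × variance gives

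lower bound = -2z² / (2n - 1 + 2z²).

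- n = 35: 7.683/76.683 = 10.02%, which fails.
- n = 36: 7.683/78.683 = 9.76%, which passes.

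So 36 is the minimum, as Table 5 states for 100% versus 100%. Exact enumeration also reproduces the pertussis rows: power is 99.3% (FHA, 212), 99.2% (PT, 276) and 99.1% (PRN, 367).

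**2. Lower bound after a collapse.** By the same formula:
- n = 212: 7.683/430.683, so -1.78%.
- n = 276: 7.683/558.683, so -1.38%.
- n = 367: 7.683/740.683, so -1.04%.

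All are far above -10%, and none depends on the 20vPnC results.

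**3. Where the boundary lies.** 5% of n is 10.6, 13.8 and 18.35, so the cut-off collapses from 11/212 (5.19%), 14/276 (5.07%) or 19/367 (5.18%) below the LLOQ under an empirical-distribution percentile. With linear interpolation the cut-off at 14/276 or 19/367 still lies above 0.5 × LLOQ, and the collapse starts one infant later (15/276 = 5.43%, 20/367 = 5.45%).

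**4. Chance of collapse.** Binomial probability of more than floor(0.05n) below-LLOQ results among n 13vPnC infants. In brackets: boundary one infant later.

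| Assumed true rate | n = 212 | n = 276 | n = 367 |
|---|---|---|---|
| 1% | <0.01% | <0.01% | <0.01% |
| 2% | 0.4% (0.1%) | 0.2% (0.1%) | <0.1% (<0.1%) |
| 3% | 6% (3%) | 4% (2%) | 2% (1%) |
| 4% | 23% (15%) | 22% (14%) | 15% (10%) |
| 5% | 49% (37%) | 52% (41%) | 47% (38%) |

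**5. Constructed example, n = 367.** Take 22 below-LLOQ infants in 13vPnC (6.0%) and 73 in 20vPnC (19.9%).
- Rules applied to the analysis values: 367/367 versus 367/367, lower bound -1.04%, noninferior.
- Cut-off floored at the LLOQ: 294/367 (80.1%) versus 345/367 (94.0%), lower bound -18.8%, fails.
- With only 15 below the LLOQ in 13vPnC (4.1%) and the same 73 in 20vPnC, the unfloored rule works: the lower bound is about -21%, which fails.

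**The case against.** The strongest reply is that nothing in the documents puts the below-LLOQ rate near 5% one month after three doses. Table 5 takes its 13vPnC percentages and group differences from two earlier Phase 3 studies and assumes PT 94/95, FHA 95/95 and PRN 93/95. A collapsed cut-off would have given 100/100. This stands, with one caveat: the documents do not say that those studies used the same assays or LLOQs.

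Second, the definition speaks of a concentration that was observed and achieved, and SAP 5.3 separates reported from imputed values. An imputed value is arguably neither observed nor achieved. On that reading the cut-off is undefined once more than 5% are below the LLOQ, and the antigen does not pass automatically. That is a fair alternative, but it still leaves a gap in a primary decision rule.

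Third, a reader might infer that real interference would go unseen. The documents do not support that. SAP 6.1.3.1.1 requires counts and percentages by group, so 100% versus 100% on a cut-off meant to give about 95% would stand out. SAP 5.2.2.1 also provides geometric means with intervals for the concomitant antigens. Neither carries a decision rule for pertussis, so the formal result would still be noninferior.

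Fourth, some text next to these rules is redacted, including text directly after the pertussis definition in protocol 8.1.1. The absence of a safeguard can be asserted only for the visible text.

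**Conclusion.** The gap is real but conditional, and minor. If the cut-off is computed from the analysis values and more than about 5% of tested 13vPnC infants are below the LLOQ for PT, FHA or PRN, that antigen's test cannot fail. The boundary moves by about one infant with the unspecified percentile method. Only the affected antigen passes automatically; the other antigens must still pass for the objective to be met.

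It would be tempting to conclude that the pertussis tests are likely to be empty. The documents do not support that. They give no LLOQ or below-LLOQ rate, Table 5 points to working cut-offs in the earlier studies, and the chance is negligible at a true rate of 1% and at most 0.4% at 2% for these sizes. It becomes material only from about 3% to 4% upward. The case for acting is that a safeguard written now is prespecified, whereas one written after a collapse is not.

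**What to change.** In SAP 3.1.3 and protocol 9.1.2.2.1:
- Define the pertussis cut-off as the larger of the assay LLOQ and the concentration reached by 95% of 13vPnC recipients.
- State the percentile method.
- State that a below-LLOQ result never counts as reaching the cut-off.
- When the LLOQ applies, report the actual 13vPnC percentage in place of the nominal 95%.

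The cost is a sentence or two in each document. The floor changes no infant's classification whenever the cut-off already lies above 0.5 × LLOQ: quantifiable results are not below the LLOQ, and substituted ones fail either way. The one downside arises when the floor applies. 13vPnC attainment is then below 95%, so power for that antigen is somewhat lower than Table 5 shows.
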